## Consent Procedures

We will e-mail or mail the Consent Form along with baseline research questionnaires to prospective participants who agree to participate in the study. The consent form will be accompanied with an information letter stating that they should read the consent form carefully and call us if they have any questions before signing the form. They can e-sign and return the form via e-mail, send a scanned consent paper via e-mail, or send a picture of a signed consent form via telephone message. For individuals who do not have e-mail account or prefer the form via post office mail, we will ask them to return the signed consent form in a self-addressed stamped envelope that will be provided. [name] or [name] will make a one-time call to remind them of returning the consent form if they have not done so within the next two weeks. [name] will be available by telephone to help them complete the form if they have any questions about it. Women who have not returned the signed consent form after the reminder call will be considered “not interested” in the study and their screening data will be shredded.

## Intervention Procedure

The quit day will be determined between the second and fourth sessions based on one’s readiness for quitting. The first three sessions is focused on preparing participants for the quit day. A female therapist ([name] and [name]) will educate neurobiological changes in the brain associated with nicotine addiction and how nicotine patches help them quit smoking. She will also train participants to learn behavioral strategies that have been found effective for dealing with symptoms of nicotine withdrawal. Post-quit sessions vary by individual needs depending on their abstinence status and severity of nicotine withdrawal symptoms. Below is the description of intervention components for each session in both videoconferencing and telephone counseling interventions.

Table 1. Intervention components of each session

Session	Intervention Components
1st session	Assessment and Planning: Assess decisional balance between pros and cons of smoking; discuss and select the target quit date; discuss how to change one’s smoking pattern for quitting; assign a homework to do an hourly smoking log sheet; provide information what has been reported in tobacco literature on people with HIV infection; and instill hope that smoking cessation is possible with guidance and support.
2nd session	Health Benefits of Quitting: Assess the participant’s perceived health status, discuss immediate health benefits of quitting smoking; explain smoking increases bacterial and Pneumocystis pneumonia among people with HIV infection; inform women with HIV infection who smoke are more likely to develop AIDS and die from AIDS-related cancers and infections than those who don’t smoke; and encourage her to watch CDC’s Tips from Former Smokers: Smoking and HIV.
3rd session	Preparation for the Quit Day: Explain the neurobiological change of brain associated with nicotine dependence; explain nicotine patches, effects and side effects of the medication and how to manage side effects if they occur; counsel behavior changes in preparation for the target quit day; explain possible drug-to drug interactions between nicotine patches and HIV medications; and advise to download a free smartphone quit application such as QuitPal and StayQuit Coach.
4 th session	Nicotine withdrawal symptoms and Medication Management: Assess nicotine withdrawal symptoms, lapse/relapse, adherence to nicotine patches, and any side effects of nicotine patches; advise proper managements of any patch problems; and counsel behavioral coping strategies for the withdrawal symptoms.
5th session	Lapses and Relapse: Assess nicotine withdrawal symptoms and lapses and relapse; discuss helpful cessation strategies including 4 Ds (delay, deep breathing, drink water, and discuss); and discuss about HIV smokers who courageously beat the deadly addiction.
6th session	Stress and Coping Skills: Assess nicotine withdrawal symptoms and lapses and relapse; counsel to understand the effects of negative cognitions on negative moods (e.g., depression and anxiety), discuss positive coping skills; discuss any positive changes in the body; and encourage exercise and healthy living.

7 th Session	Medication Adherence: Assess medication adherence; explain the importance of adherence to nicotine patches; and explain about dose reduction of nicotine patches (from step 1, 21mg to step 2, 14mg).
8 th session	Relapse Prevention: Discuss strategies to avoid lapses and relapse in high risk situations (e.g., meeting a friend with whom the participant used to smoke); and revisit the importance of quitting smoking and medication adherence.

Participants in both arms will receive nicotine patches at two separate occasions: first, a 4-week supply of 21mg nicotine patches (14 mg if the participant smoke 5-9 cigarettes per day) and second, a 2-week supply of 14mg nicotine patches and a 2-week supply of 7mg nicotine patches together. All participants will also have education about the pharmacological mechanism of nicotine patches and their correct usage and management of possible side effects. Adherence to the medication will be monitored by asking participants to show used patches within the past week for the video arm and by asking participants the number of patches that have been used within the past week for the telephone arm.

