### III. Methodology.

The proposed study is a 2-arm parallel-group RCT of a smoking cessation intervention with 50 English-speaking women who have been diagnosed with HIV infection. Participants will be randomized at a ratio of 1:1 to either the video arm (n = 25) or the telephone arm (n = 25). The randomization will be based on computer-generated random numbers (<http://www.randomizer.org/>). The numbers will be written in a color-coded paper (the video arm = red and the control arm = blue). These papers will be placed in an envelope in order, which will be open right after the completion of the baseline assessment. Both arms will have eight weekly individualized counseling sessions and each session will be 30 minutes long. The study is conducted to determine the acceptability and feasibility of a videoconferencing smoking cessation intervention for women with HIV. It is also being conducted to estimate the effect of the videoconferencing smoking cessation intervention on abstinence compared with telephone counseling cessation intervention for women with HIV.

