**The following screening interview script will be used:**

1. Can you speak English? Yes
2. Have you been diagnosed with HIV infection? Yes
3. What kind of medications are you currently taking for HIV infection? (This question is asked as a way to verify HIV infection)
4. How old are you? 18 or older
5. How many cigarettes on average have you been smoking a day? 5 or more cigarettes per day
6. How long have you been smoking? At least for the past 6 months
7. Are you willing to quit smoking within the next four weeks? Yes
8. Are you willing to use nicotine patches? Yes
9. Do you have any active skin disease? No
10. Have you had emotional complications such as feeling anxious and depressed around quitting smoking?  
No. If the caller answers “yes” to this question, we will ask whether the quit attempt was made with or without assistance. We will also ask the severity of the complication(s). If the caller answers that the complications were so distressing and required treatment, she will be excluded from the study.
11. Do you currently receive treatments (counseling and pharmacotherapy) for any of these conditions: Suicidal Ideation, Alcohol Dependence, Schizophrenia, Schizoaffective Disorder, and Bipolar Disorder?  
No
12. Have you ever attempted to kill yourself? No
13. Do you currently use any illegal substances except marijuana (weed)? No
14. Are you pregnant? No
15. Are you currently using any method of birth control? Yes. We will then ask the caller to specify what type of birth control she is currently practicing. If no, we will ask whether the caller is willing to practice birth control during the intervention period (3 months). Only those who use or agree to use an approved form of birth control (e.g., oral medications, condoms, Depo Provera injection, and intrauterine devices) will be accepted into the study.
16. Are you currently breast-feeding? No
17. Do you agree to use birth control pills or devices during the study period? Yes
18. Do you have access to a telephone and an Internet-connected computer? Yes

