#### **IV. Participant**

**Inclusion criteria.** To participate in this study, an individual must be a woman who: (1) is able to speak English, (2) self-reports having been diagnosed with HIV infection, (3) is between the ages of 18 and 75, (4) has smoked at least 5 cigarettes per day for the past 6 months, (5) has access to smartphone and computer (a desktop or laptop) with Internet/wireless, (6) is willing to quit smoking within the next 4 weeks from the first session of counseling, and (7) agrees to use an approved form of birth control during the intervention.

**Exclusion criteria.** Individuals will be excluded based on any of the following criteria: (1) current involvement in other behavioral or pharmacological smoking reduction/cessation programs, (2) being pregnant or lactating, (3) active skin diseases, (4) serious alcohol use problems or current use of any illegal substances, or (5) active treatment for serious mental illness such as schizophrenia and bipolar I disorder.

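### Does it matter that session 7 names only a 21 mg to 14 mg step-down, when women smoking 5-9 cigarettes a day are supplied no 21 mg patches?

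*Protocol*

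**What the plan says.** All the main text is in the protocol's Intervention Procedure section.

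- **Table 1, 7th session.** After assessing adherence and stressing its importance, the counsellor is to "explain about dose reduction of nicotine patches (from step 1, 21mg to step 2, 14mg". The table is introduced as applying to both arms and has no version by smoking level.
- **Patch-supply paragraph, first supply.** Participants receive "a 4-week supply of 21mg nicotine patches (14 mg if the participant smoke 5-9 cigarettes per day".
- **Patch-supply paragraph, second supply.** Participants receive "a 2-week supply of 14mg nicotine patches and a 2-week supply of 7mg nicotine patches together". No variant by smoking level is stated.
- **Eligibility.** Inclusion criterion 4 in section IV. Participant requires that a woman "has smoked at least 5 cigarettes per day for the past 6 months". The screening script sets the same floor, "5 or more cigarettes per day".

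Other text governs how the sessions are delivered. Section III. Methodology states: "Both arms will have eight weekly individualized counseling sessions". Intervention Procedure adds: "Post-quit sessions vary by individual needs depending on their abstinence status and severity of nicotine withdrawal symptoms". On patch instruction it says: "All participants will also have education about the pharmacological mechanism of nicotine patches and their correct usage and management of possible side effects". It also says how adherence is monitored: video-arm participants display the patches they have used over the preceding week, while telephone-arm participants report only how many they used.

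**The concern.** Read alone, the session 7 row describes a single step-down that starts from 21 mg. A few lines later, the supply paragraph starts a whole eligible subgroup on 14 mg. For those women, the strength that the row calls step 2 is the one they begin with.

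If a counsellor delivered the row literally, a woman would be told about a reduction from a patch she never had, in the session devoted to medication adherence. That would raise two questions: whether the information given to participants is correct, and whether the counselling is delivered consistently. In a trial with 25 women per arm that compares two ways of delivering the same counselling, a reviewer would also want to know whether such a slip could affect the comparison of abstinence between arms.

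**Working it through.** The plan states no figure to reproduce on this point. The check tallies patch-weeks from the supply paragraph and sets them against the session 7 row.

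**Inputs.** The first supply lasts 4 weeks, at 21 mg, or 14 mg for women smoking 5-9 a day. The second supply is 2 weeks of 14 mg plus 2 weeks of 7 mg. The entry floor is 5 cigarettes a day, so everyone outside the 5-9 group smokes 10 or more.

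**Assumption.** The second supply is the same for both groups. This is the natural reading, since no variant is given, but the text does not say so outright.

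| | 10 or more a day | 5-9 a day |
|---|---|---|
| Weeks at 21 mg | 4 | 0 |
| Weeks at 14 mg | 2 | 4 + 2 = 6 |
| Weeks at 7 mg | 2 | 2 |
| Total weeks | 4 + 2 + 2 = 8 | 0 + 6 + 2 = 8 |
| Change at the start of the second supply | 21 − 14 = 7 mg lower | 14 − 14 = 0 |
| Steps down | 21 to 14, then 14 to 7 | 14 to 7 only |

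The step named in session 7 therefore occurs in the first pattern and not in the second. If the second supply did differ for the 5-9 group, the 6-week and 2-week split would change, but nothing in the text suggests that these women would receive 21 mg.

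**How many women.** The documents do not give the expected share of women smoking 5-9 a day. It could be anything from none to all of the 50, so the number affected cannot be estimated.

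**What could change in the results.**

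1. The SAP's outcomes are 6-month prolonged abstinence, 7-day point prevalence abstinence, times to first lapse and to relapse, recovery from relapse, and changes in self-efficacy, depressive symptoms and anxiety symptoms. Patch strength and patch adherence are not among them.
2. No analysis in the SAP is defined by patch strength or by the content of session 7.
3. Table 1 and the supply paragraph apply to both arms, and allocation is random at 1:1. Neither arm is expected to contain more women from the 5-9 group, apart from chance imbalance.
4. These women hold no 21 mg patches, so the session 7 wording cannot lead them to use study-supplied patches of that strength.

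**How the row would be used.** Its instruction is to explain dose reduction, and the strengths are in parentheses. The supply paragraph gives the same 21 mg default together with its exception. With a quit day between sessions 2 and 4, session 7 falls after quitting, where content is allowed to vary with the participant's needs. For a counsellor to give the wrong explanation, she would have to recite the parenthesis without regard to the supply that the woman has been sent.

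**The case for a change.** The strongest case for a change is that none of the softening text actually alters the session 7 row.

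- Rows 6 and 8 of the same table mark their illustrations as examples. Row 7 does not, and it names specific steps and strengths.
- The sentence on flexibility after the quit day ties it to abstinence status and withdrawal severity, and does not mention patch strength.
- General teaching on patch use does not spell out the step-down for the 5-9 group.
- One of the counsellors is a doctoral student, for whom exact written content is helpful.
- The remedy would cost only a few words.

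There is also a difference between the arms. A video counsellor can see the used patches and notice a discrepancy, while a telephone counsellor hears only a count. The safeguard is therefore weaker in the telephone arm.

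Most of this stands as an account of the wording. The two texts do not match for the 5-9 group, and neither of them resolves the mismatch expressly. It does not establish a consequence. The row nowhere says that the parenthesis applies at every smoking level, and the exception appears in the same section. That makes a default followed by its variant the more sensible reading. The difference in what counsellors can see belongs to the comparison of video with telephone, and it would exist whatever the row said. Low cost alone does not turn a wording slip into a defect of the plan.

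**Conclusion.** The inconsistency is genuine but clerical, and no change to the plan follows. Session 7 illustrates dose reduction with the default strengths only. The supply paragraph gives women smoking 5-9 a day 0 of 8 weeks at 21 mg, so the illustration does not fit them. Individualized sessions, patch education for all and, in the video arm, sight of the used patches make it unlikely that a woman would be misinformed. The effect on endpoints, analyses and statistical figures is nil, and no safety consequence is shown.

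This rests on three things: the second supply being the same for both smoking levels, counsellors working from the patches each woman has been sent, and the text available for this check. Part of the protocol directly after the supply paragraph was not available, and it may bear on the point. The share of women affected is unknown, but the conclusion does not depend on it.

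The session 7 parenthesis and the supply paragraph remain for the sponsor to reconcile as a point of wording. Nothing here indicates which strength or schedule is right.

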### Counselors

[name] and [name] (a doctoral student in nursing) will provide cessation counseling. Prior to providing counseling, [name] will have intensive trainings of tobacco dependence treatment and telephone cessation counseling. The trainings also include role-playing scenarios of common problems.

### Follow-up Assessment

Women who have not returned a signed consent form will not participate in any follow-up assessment. Only participants who provide the consent form and report abstinence at 3-, and 6-month follow-ups will be asked to perform a saliva cotinine test via video calls. The tests are done only after the completion of counseling and nicotine replacement therapy and those in the telephone arm will also perform the saliva test via video calls (the video call is done for the test not as part of the intervention). For this, they will receive the saliva test kit via certified mail. Cotinine is the major proximate metabolite of nicotine. It has a long half-life approximately 15-19 hours and is widely used as a biological marker of nicotine exposure [18]. In this study, we will use the NicAlert® test that is a semi-quantitative measure of cotinine based on colorimetric immunoassay reaction. The test strip displays seven zones that represent a range of cotinine levels from 0 (0–10 ng/ml) to 6 ( $\geq 2000$  ng/ml). Those who earn level 1 or higher will be treated as smoking irrespective of their self-report. Participants will also be assessed on the measures of self-efficacy in resisting smoking temptation, depression and anxiety to see any changes since baseline.

Participants will receive a gift card worth \$30 at baseline and \$25 at each of the three follow-up assessments (post-quit 1-, 3-, and 6-months) irrespective of their smoking status (abstinent vs. smoking). If they perform the saliva test, they will receive an additional gift card worth \$25. Thus, those who perform the test will receive a gift card worth \$50 at each time. The gift card will be mailed to the home address via a postage mail.

The study is a pilot project to obtain preliminary data for the feasibility and acceptability of a videoconferencing smoking cessation intervention for women living with HIV. [name] will identify and describe the time to recruitment and any barriers. She will also describe reasons for any refusals to study participation. She will compare abstinence and attrition rates at each follow-up. Participants will complete an Exit Survey, rating their overall satisfaction with the intervention that they have.

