#### **V. Risks and Benefits**

Reasonably foreseen risks involved in this study are symptoms of nicotine withdrawal and potential side effects of nicotine patches, although these are recognized as relatively safe. Nicotine patch is one of the FDA approved first-line cessation medications and can be purchased over the counter without a prescription [6]. The most common adverse effect of the patch is topical skin irritation, ranging from mild erythema to a more generalized skin reaction, frequently in participants with a history of eczematous dermatitis. Other potential side effects include nausea, vomiting, headache, light headedness, rapid heartbeat, and strange dreams. However, all of these side effects occur at about 10-15% and mostly are mild. They will disappear once a person stops using the medication. Another potential risk that may occur is related to the loss of privacy or breach of confidentiality. There is also a potential risk of embarrassment among those who report abstinence but their saliva cotinine test yields a positive result. False positive results are possible if participants have been exposed to secondhand smoke. In the rare event that a participant may express suicidal ideation. If this happens, [name] will evaluate the participant to assess suicidality of the participant using the Columbia-Suicide Severity Rating Scale (C-SSRS). If the counselor is [name], she will immediately contact [name] at [contact] for evaluation who will evaluate the person within the next 2 hours. If the person is determined to be at immediate danger, [name] will inform that she has to break confidentiality and call 911. If the participant is not determined to be at immediate risk, [name] will strongly encourage the person to talk to her primary healthcare provider or call the Suicide Hotline if she has suicidal ideation. [name] will follow up on the person weekly for the next month and then monthly until the person completes the study.

**Potential benefits.** Participants may benefit because they will receive an evidence-based tobacco dependence treatment that has been developed and found effective in the general U.S. population when it is delivered via person-to-person. Their family members may also benefit if participants quit smoking because they are less likely to be exposed to secondhand smoke.

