Study Title: Smoking Cessation Intervention for Women Living with HIV
NCT NO: NCT02898597

January 31, 2017

Data Analysis Plan

Data will be reviewed prior to data entry and entered by a research coordinator, which will be double-checked for errors or completeness by a third person. Data will be analyzed using Stata 14 (Stata Corp LP, College Station, TX, USA). Intention-to-treat analytic strategy will be used for cessation outcomes with missing values. The primary outcome of the study will be a 6-month prolonged abstinence. Its secondary outcomes will include 7-day point prevalence abstinence at each follow-up (1, 3, and 6 months post-quit), time to the first lapse, time to relapse, recovery rates from smoking relapse as well as changes in self-efficacy, depressive symptoms, and anxiety symptoms between the two treatment conditions and over time (baseline and 3- and 6-month follow-ups).

Specific aim 1: test the feasibility and acceptability of a videoconferencing smoking cessation intervention for women with HIV.

Recruitment and retention rates will be recorded per month throughout the study period. Any barriers to the recruitment and retention will be explored. Reasons for those who are eligible but decline to participate in the study will be recorded. Attrition rates will be compared by intervention condition and abstinence status at each follow-up. All participants will be asked to complete an exit survey, rating their overall satisfaction with the intervention that they have received.

Specific aim 2: establish a preliminary effect size of the videoconferencing smoking cessation intervention on 6-month prolonged abstinence compared to the telephone-based smoking cessation intervention.

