The balance of participants' baseline demographics and smoking behavior between the two treatment conditions (videoconferencing vs. telephone counseling) will be evaluated using Mann–Whitney U tests or independent two-sample t-tests for continuous variables and the χ^2 tests for categorical variables. Contingency analysis with χ^2 test will be used to examine differences in the 6-month prolonged and 7-day point prevalence abstinence at each follow-up between the two arms. Survival analyses will be conducted to examine the relationship between the two arms and abstinence using the Kaplan–Meier survival plot and Cox proportional hazards model for possible covariates such as nicotine dependence and self-efficacy. Based on the intention-to-treat analysis, those who are missing at follow-ups will be treated as smoking. Participants who self-report abstinence but yield a positive result (cotinine concentration ≥ 10 ng/mL) or refuse to do the salivary cotinine test for any reasons will be all treated as smoking. An effect size will be calculated by comparing the 6-month prolonged abstinence rates between the two arms.

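### No check of nicotine-product use is described at the cotinine test, so a non-smoking woman with use in about the last 6 days would be coded as smoking

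*Protocol*

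**What the plan says.** All participants receive nicotine patches: a 4-week supply, then 2 + 2 weeks sent together (Protocol, Intervention Procedure, after Table 1). Follow-ups are at 1, 3 and 6 months after quitting. Consenting women who "report abstinence at 3-, and 6-month follow-ups will be asked to perform a saliva cotinine test via video calls" are the only ones tested; there is no strip at 1 month.

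Three statements govern the strip:

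- **Timing** (Protocol, Follow-up Assessment): "The tests are done only after the completion of counseling and nicotine replacement therapy".
- **Coding** (same section): "Those who earn level 1 or higher will be treated as smoking irrespective of their self-report".
- **Coding in the SAP** (Specific aim 2): "Participants who self-report abstinence but yield a positive result (cotinine concentration ≥ 10 ng/mL", together with women who "refuse to do the salivary cotinine test for any reasons will be all treated as smoking".

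The Protocol describes cotinine as a product of nicotine metabolism and an indicator of exposure to nicotine, with a half-life of about 15–19 hours. Its risk section names secondhand smoke as a source of false positives and does not mention nicotine replacement there. The same section notes that patches "can be purchased over the counter without a prescription". The SAP's secondary outcomes include "recovery rates from smoking relapse".

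**The concern.** Cotinine shows that nicotine was taken in, not that a cigarette was smoked. The plan separates the two by timing alone: the test should come after replacement has ended. The available text does not say how the caller confirms that it has ended, or what happens if it has not. Both coding rules are absolute, so a positive strip overrides a truthful report of not smoking.

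Off-schedule use is foreseeable. Lapse and relapse are counselled in several sessions, recovery after relapse is a planned outcome, and patches can be bought freely. The quit day falls between the second and fourth of eight weekly sessions. If patches start on that day (an assumption), an 8-week course ends about 2–4 weeks after the last session. The Protocol describes weekly monitoring of patch use but does not say that it continues to the 3- and 6-month tests.

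At stake are the strip-verified abstinence rates at 3 and 6 months and, depending on its definition, the effect size that Specific aim 2 is meant to produce.

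**Working it through.** The plan states no figure for this, so there is none to reproduce. Four checks follow.

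**1. Does the supplied course end before the strip?** Supply is (4 + 2 + 2) × 7 = 56 days. Three months is about 91 days and six months about 183. If patches start at the quit day and are used as supplied (assumption), they end 91 − 56 = 35 days before the first strip and 183 − 56 = 127 days before the second. Counting three months as 84 days, the first gap is 28 days. An uninterrupted course would have to start about 35 days or more after the quit date to be still running at day 91.

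**2. How recent must use be to give a positive strip?** Days to fall below 10 ng/mL = log2(C0/10) × half-life / 24, with the Protocol's 15–19 h. The starting levels C0 are assumptions; 2000 ng/mL is the lower bound of the strip's top zone.

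| C0 (ng/mL) | Half-lives | Days at 15 h | Days at 19 h |
|---|---|---|---|
| 100 | 3.32 | 2.1 | 2.6 |
| 300 | 4.91 | 3.1 | 3.9 |
| 2000 | 7.64 | 4.8 | 6.1 |

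Only use in about the last 6 days matters. A 7-day wait is 168/19 = 8.8 half-lives at the slow end, about a 460-fold fall, so 2000 ng/mL drops to about 4 ng/mL.

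**3. What does one case do?** 1/25 = 4 percentage points. At 7/25 = 28% (the lower end of the earlier videoconferencing pilot's 28–30%), one miscoded woman gives 6/25 = 24% and two give 5/25 = 20%.

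**4. What happens to the comparison?** Assume true rates of 28% and 8% (2/25, inside the 6–9% that the Protocol quotes for existing interventions). Let f be the fraction of true abstainers miscoded.

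- Same f in both arms: RD = (0.28 − 0.08)(1 − f); RR = 0.28/0.08 = 3.5 for any f.
- Video arm only: RD = 0.28(1 − f) − 0.08; RR = 0.28(1 − f)/0.08.

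| f | RD, both arms | RR, both arms | RD, video only | RR, video only |
|---|---|---|---|---|
| 0 | 0.20 | 3.5 | 0.20 | 3.5 |
| 0.10 | 0.18 | 3.5 | 0.172 | 3.15 |
| 0.20 | 0.16 | 3.5 | 0.144 | 2.80 |
| 0.30 | 0.14 | 3.5 | 0.116 | 2.45 |

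The documents give no value for f, so the table shows sensitivity and is not an estimate.

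**The case against.** The strongest reply is that the Protocol has already dealt with this. Strips come after replacement is finished, the schedule leaves about five weeks of slack, and cotinine clears within days. The coding rule is prespecified, conservative and the same in both arms, and this is a 50-woman pilot. For women on schedule that reply is right, and it answers several stronger readings that a reader might infer:

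- *Women on study patches will be coded as smokers.* Not if the patches are used as supplied (check 1).
- *The timing and coding rules contradict each other.* They apply in sequence: first when to test, then how to code. What is lacking is a way to confirm that the timing condition is met.
- *Any purchased product causes an error.* Product finished more than about 6 days before the strip does not (check 2).
- *Product use is not recorded.* This cannot be established: the follow-up questionnaires are not in the available text. One can say only that no check at the test is described there.
- *The recovery rate and the primary outcome are biased downwards.* The available text defines neither how recovery is verified nor how the 3-month strip enters prolonged abstinence. A woman who re-quits after relapse would ordinarily have failed prolonged abstinence already.
- *The arms are biased against each other.* Both get the same supply. Adherence is monitored differently (used patches shown on video, a number reported by telephone), which makes a difference in use conceivable but does not demonstrate one.

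What survives is the woman outside the schedule. If the timing sentence is an operating rule, the available text gives no step for applying it; if it is only an expectation, her positive strip is scored as smoking.

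**Conclusion.** The point holds in a limited form. Women who use study patches on schedule are covered. A non-smoking woman who used late, restarted or self-bought nicotine within about 6 days of a 3- or 6-month strip, and whose cotinine is still at or above the cutoff, would be coded as smoking, and no described step would detect it. Each case costs her arm 4 percentage points on the verified outcome concerned. Equal proportional miscoding lowers both rates and the risk difference and leaves the risk ratio alone; bias between arms requires unequal product use at the test. Effects on prolonged abstinence and on recovery depend on definitions that the available text does not give.

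The conclusion rests on the Protocol's half-life, on assumed starting levels up to 2000 ng/mL, and on patches starting at the quit day. The number of women affected is unknown and may be small. The change is still worth making, because product use not asked about at the test is hard to recover later.

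**What to change.** Amend the Protocol's Follow-up Assessment and the SAP's Specific aim 2:

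1. At the 3- and 6-month test calls, before the strip is read, record any use of a nicotine product in the past 7 days and the date of last use.
2. Where use has already ended, apply the Protocol's own timing rule by taking the strip at least 7 days after last use. State that a strip deferred for this reason and then taken is not a refusal. Do not ask any woman to stop a product for the sake of the test.
3. Keep a positive strip coded as smoking in the primary analysis. Add one prespecified sensitivity analysis, reported by arm, that counts as abstinent the women who report abstinence, have a positive strip and have recorded product use.

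The cost is a short question at each test call, an occasional rescheduled strip and one extra row in the results. The downside is that a few outcomes rest on self-report, in the sensitivity analysis only.
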